regimens will result in optimization of GDMT medications compared to usual care and we will demonstrate the safety and utility of using CIED data for patient management. Furthermore, we would like to provide evidence that remote interactions, encouraging patient engagement via virtual visits and mobile device based quality of life questionnaires, can be used to improve functional and clinical outcomes in heart failure patients.

We chose to focus this pilot study on both ischemic and non-ischemic cardiomyopathy since patients in both groups have potential for improvement following medical optimization.

Objectives

To demonstrate that a multidisciplinary team intervention (see administrative organization section) using pre-specified medication dosing standards guided by CIED-derived data will increase the rate of change in GDMT medication dosing in the intervention group compared to usual care at 6 months in cardiomyopathy patients who have received an ICD (Medtronic) for primary prevention.

The secondary objectives are:

- 1) To characterize the correlation between Cardiac Compass-guided optimization and improved functional capacity and activity
- 2) To show that ICD-derived physiologic data, including arrhythmia and activity, are associated with clinical outcomes.
- 3) To validate a personalized framework for optimizing GDMT based medication dosing using time-dependent CIED and wearable sensor derived physiologic and functional data.
- 4) To characterize the correlation between wearable wristband sensors derived activity data and functional capacity and show that activity is associated with improved clinical outcomes.
- 5) Characterize health care utilization, defined as unplanned clinic visits, emergency department utilization, and hospitalization between CIED guided GDMT and usual care.
- 6) To develop a risk stratification scheme for adverse events within the total study population using time-dependent CIED and wearable sensor-derived physiologic and functional data.
- 7) To demonstrate that remote monitoring with a concurrent patient engagement strategy, using optional journal entries, is associated with improved clinical and functional outcomes and reduced health care utilization.
- 7) Quality of life (measured by Kansas City Cardiomyopathy Questionnaire) from enrollment to 6 months.

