4. STUDY DESIGN

The study is a randomized pilot clinical trial. The Coordination and Data Center (CDC) is at the University of Rochester. Each site will directly interface with the subjects for activities such as consent, testing, study team virtual and in person-visits.

The study will enroll approximately 30 subjects with ischemic and non-ischemic cardiomyopathy previously implanted with an ICD for primary prevention of sudden cardiac death. Subjects are followed for 6 months. Clinical, functional, and digital biomarker data will be captured related to: activity, heart rate, blood pressure, weight, blood biomarker BNP, quality of life status, and clinical events. Electronic health records will be monitored for 12-month period to collect/record study data.

Study data will be entered by site staff using a web-based data entry system at the University of Rochester for data management, analysis, and coordination of logistics.

The study duration is 2.0 years: including an estimated 3-month initiation phase; an estimated 8-month enrollment phase; and an estimated 6-month follow-up phase; with subsequent data analysis.

Primary Endpoint

The primary outcome of this study is the rate of change in medical management with beta-blockers, diuretics and Sacubitril/Valsartan (defined as initiation, termination, switch, or dosing adjustment) in the intervention group compared to usual care at 6 months.

Secondary outcomes

- Recurrent changes to medication type and dosing reflecting ongoing personalized optimization.
- Mean changes in functional status (measured by 6-minute walk distance) in the intervention vs. control groups.
- Percentage change in average daily activity level between the first month following discharge and the last month of the study (6th month) will be compared between intervention and control groups.
- Quality of life (measured by Kansas City Cardiomyopathy Questionnaire) from index discharge to 6 months after discharge in the intervention vs. control groups.
- Healthcare utilization as determined by unplanned office visits and hospitalizations.
- Cardiac hospitalizations and all-cause mortality.
- Laboratory biomarkers.

Screening

Potential subjects will be screened using electronic records to ascertain prior ICD implantation per inclusion/exclusion criteria. The potential subject's health care provider will be contacted for permission to approach the patient for further screening and if eligible, obtain consent.

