Patients are randomized 2:1 into:

An Intervention Group

The clinical management of the intervention group will be comprised of the following:

- A study care-team, comprised of a Cardiologist, an Electrophysiologist, a Registered Nurse, and study coordinator who will receive monthly physiologic and functional reports derived from Medtronic CIEDs incorporating Cardiac Compass and OptiVol monitoring.

- The study team will also be provided with patient-specific data derived from patient reported outcomes that include symptoms, quality of life scores, and PROMIS data if available. PROMIS®, a tool developed for use by the National Institutes of Health provides quality of life data, and is part of standard clinical care at the University of Rochester Medical Center Cardiology Department for patients. This is a survey patients have the option of filling out at clinic visits and available through the electronic medical record.
- The Datos app platform will be used to conduct a separate Quality of Life study survey and weekly e-survey REDCap may also be used as an additional resource..
- A pre-specified management regimen based on standard clinical practice will be provided to the study team in which medical management including medication dosing (focusing on beta-blockers and diuretics) will be monitored and modified using CIED and OptiVol data (see Figure 1 and footnote* at end of document). This is based on current and accepted clinical practice.
- The study team will contact the patients on a monthly basis for 4 monthly virtual visits. Based on CIED and patient engagement data, the study team will adjust medications and dosages, and optimize activity/ exercise steps. All medication changes resulting from the virtual visits will be updated in the subject's electronic medical record and communicated by medical chart messaging or URMC email based on the patient physician's preference.
- All study team contacts with the patients will be virtual, using telecommunication or E-communication. These options include URMC approved Zoom portal (currently used for URMC telemedicine clinical care), phone, or email. If the telemedicine call (preferred method) is disconnected, phone or email will be utilized. These e-communications will occur using an existing HIPAA compliant platform to improve efficiency, patient engagement, and reduce study costs while preserving data quality.

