- In-person clinic research visits will be scheduled at 3 and 6 months, if feasible (if in-person visit is not feasible, Zoom or telephone visit will be conducted). Medication changes may occur based upon study physician judgement, assessment including NYHA class, in- person device interrogation, and patient reported symptoms.
- Garmin wearable wristband sensor data, such as number of steps, heart rate, and oxygen saturation, is passively captured and not used for patient management.
- CIED functional and physiologic data, as well the OptiVol monitor information and wristband sensor data will be captured in the study digital biomarker core-lab to better understand risk stratification in the total study population following study completion (see secondary aims above).

A Conventional Management Control Group

The clinical management of the control group will be comprised of the following:

- In-person clinic research visit, if feasible (if in-person visit is not feasible, Zoom or telephone visit will be conducted) will be scheduled at 3 and 6 months, similar to the intervention group. The 3 and 6-month visit includes: in-person device interrogation, NYHA class, any changes to medication or new events.
- To control for patient contact, patients in the conventional management group will receive 4 monthly virtual visits from the same study team. The study team will ask questions about symptoms, changes in activity levels, medication changes by their non-study

physician, and any adverse events. The study team however will not be provided with any patient specific Optivol data, survey results or PROMIS® data.

- CIED functional and physiologic data, as well the OptiVol monitor information and wearable wristband sensor data, for the control group will be captured in the study digital biomarker core-lab for the development of a risk stratification scheme in the total study population following study completion (see secondary aims above).
- The non-study physician will receive CIED/OptiVol data (as in usual care) and its use and the management strategy will be left to his/her discretion.
- The wearable wristband sensor data is passively captured and not used for patient management. Only the data currently available in remote monitoring from the ICD is being used which is same as current usual care.

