4.1. SUBJECT POPULATION

Approximately 30 subjects total will be enrolled in this study following a 2:1 ratio (intervention: control). The study will be conducted at the University of Rochester Medical Center. Over 250 patients are newly implanted with a defibrillator per year and over 1,000 patients are followed within the system.

- Gender and Age of Subjects: Male and female subjects aged 18 years to 85 years. We expect to enroll about 25% women.
- Racial and Ethnic Origin: There are no restrictions on race or ethnicity in this study. We expect to enroll about 25% minority subjects.

Inclusion Criteria

- 18 to 85 years of age on the date of randomization
- ICD implantation for primary prevention in patients with ischemic and non-ischemic cardiomyopathy ≥ 3 calendar months from date of enrollment
- SMART Phone or tablet with Bluetooth capability with internet access
- No other identifiable reversible cause explaining the left ventricular dysfunction

Exclusion Criteria

- CRT implanted.
- LVEF $> 45\%$ in the last echocardiogram or other clinic imaging performed.
- Medtronic device generator and/or device components not implanted
- Unstable clinical condition, life threatening arrhythmia
- Heart failure hospitalization within the preceding 3 calendar months
- Cognitive impairment
- Severe renal dysfunction (eGFR < 30 ml/min/m²)

- Serious known concomitant disease with a life expectancy of < 12 calendar months
- Non-ambulatory NYHA class IV
- Pregnancy

Inclusion of Vulnerable Populations:

- Vulnerable populations: Women of childbearing potential are included if they are currently on the medications to be optimized (beta-blockers, diuretics and Sacubitril/Valsartan).

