Dose adjustment will be based upon the monthly reporting of data acquired from the CIEDs focusing on the following medications: Loop diuretics (e.g., furosemide, bumetanide, torsemide) unless the subject is not indicated, is contraindicated, or is intolerant of loop diuretics; and beta-blockers unless the subject is not indicated, contraindicated, or is intolerant of beta-blockers. The choice of selective or non-selective beta-blockers use is left to the clinician Investigator's discretion. Blood work may be ordered to assess kidney function within 1-2 weeks of changes to diuretic medications.

Additional virtual follow up after dose adjustments is not prohibited and left to investigator team discretion as needed.

Figure 1: Medication Flowchart

Medication Decision Module

Medication Optimization Guideline

- If Average HR > 70 bpm + Stable OptiVol + Stable per patient symptoms, Then increase BB per the recommendation (drug dosage table)
- If Average HR < 60 bpm + Stable OptiVol + Stable per patient symptoms, Then no change in BB until next follow up
- If Average HR > 70 bpm + increased volume per OptiVol + reduction in capacity per patient symptoms, then adjust diuretics first and subsequently (in the next virtual visit BB if HF still >70 bpm)
- If Average HR < 70 + increased volume per OptiVol + reduction in capacity per CIED activity and patient symptoms, then, adjust diuretics without BB
- Similar flow process for Activity guided exercise prescription which would look to optimize daily activity/exercise steps upward toward target if OptiVol, HR, patient reported symptoms are consistent that no acute decompensation is occurring or imminent.

Clinical Discretion applies to all medication adjustments

Plans for return of research results:

- A summary of the study research results will be provided to all patients after completion of the study, analysis and publication of a peer-reviewed publication. Raw data and individual will not be available.
- For both groups, if there are life-threatening incidental findings during the study which require clinical intervention, the subject's primary clinical team will be notified in a time frame appropriate for the clinical event, via eRecord, secured email, or in person as applicable. It is understood that the usual care control group will have significantly less monitoring and data will not be analyzed at the same frequency as the intervention group.

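### The activity outcome is measured from a discharge that this trial does not have, and its between-arm contrast reflects medication plus exercise advice, not medication alone

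*Combined protocol and SAP*

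**What the plan says.** **The outcome.** Section 4 (Secondary outcomes) defines the activity outcome as "Percentage change in average daily activity level between the first month following discharge and the last month of the study (6th month"), compared between arms. It does not define discharge, and it does not say whether activity comes from the CIED or the Garmin wristband.

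**The population.** Section 4.1 requires "ICD implantation for primary prevention in patients with ischemic and non-ischemic cardiomyopathy ≥ 3 calendar months from date of enrollment" and excludes "Heart failure hospitalization within the preceding 3 calendar months".

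**Who is advised on activity.** For the intervention arm, Section 4 says: "Based on CIED and patient engagement data, the study team will adjust medications and dosages, and optimize activity/ exercise steps". Figure 1 in Section 7 adds: "Similar flow process for Activity guided exercise prescription which would look to optimize daily activity/exercise steps upward toward target", subject to there being no sign of decompensation and to clinical discretion. For controls, Section 4 says: "The study team will ask questions about symptoms, changes in activity levels, medication changes by their non-study" physician, and about adverse events.

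**The objective.** Secondary objective 1 in Section 2 is: "To characterize the correlation between Cardiac Compass-guided optimization and improved functional capacity and activity".

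**The analysis.** Section 17 gives no method for activity or 6-minute walk distance.

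**The concern.** Two features make the activity result hard to read.

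First, a change score needs a reference that is defined for every subject and that treatment cannot have altered. Here the reference is tied to an event that is not part of the trial. Depending on how the word is read, the reference month comes either after randomisation or at an uncontrolled time before enrollment. In the first case, any early effect of the intervention enters the denominator and shrinks the reported difference.

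Second, the study team works to raise activity in one arm, and activity is then compared as an outcome. Walking capacity is exposed to the same advice. Sections 2, 7 and 10 mostly describe the intervention as medication management, so a reader could credit a rise in activity to better drug therapy when it partly reflects advice to be more active.

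The two features push in opposite directions: exercise advice adds a non-drug route to higher activity, and a late reference reduces the visible change. There is no reason to expect them to cancel.

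**Working it through.** The plan states no effect size, variance or sample size for activity or 6-minute walk, so it has no figure to reproduce. The check is of timing, followed by an illustration.

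**1. What could discharge mean?**
- *Study start.* Section 2 lists quality of life by KCCQ from enrollment to 6 months. Section 4 lists the same measure from an index discharge to 6 months afterwards. KCCQ is collected only at enrollment and at 6 months (Section 7, schedule), so discharge stands in for enrollment there. The activity outcome also calls month 6 the study's last month, which counts from study start. The schedule ticks randomisation in the enrollment column, so month 1 would follow randomisation.
- *Implant discharge.* Section 4.2 describes people qualifying once an ICD has been decided on, and Section 5 mentions recent implants. Section 4.1 sets a minimum of 3 months from implant and no maximum. The reference month would then normally precede enrollment by an interval that differs between subjects. No Garmin data would exist, because the wristband is issued at enrollment.

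**2. Overlap under the study-start reading.** The first monthly virtual visit is at 1 month ± 7 days. Taking a month as 30 days, that is day 23 to day 37. The share of the reference month after the visit is max(0, 30 − day)/30:
- day 23: 7/30 = 23.3%
- day 30: 0%
- day 37: 0%

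Section 4 specifies four monthly virtual visits, and the schedule ticks months 1, 2, 4 and 5, which makes four. The further tick at enrollment is a fifth contact with no stated content. If it delivered activity advice, the share could reach 100%. Section 7 also allows extra virtual follow-up after dose adjustments.

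**3. Effect on the percentage change.** Let g be the true rise by month 6, and f the share of that rise already present in the average of the reference month. The observed change is (1 + g)/(1 + f·g) − 1. Neither g nor f is given in the documents, so both are assumed. For an immediate, sustained rise at a day-23 visit, f = 7/30:
- g = 10%: 1.10/1.0233 − 1 = 7.5%
- g = 20%: 1.20/1.0467 − 1 = 14.6%
- g = 30%: 1.30/1.07 − 1 = 21.5%

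Counting the visit day itself as exposed (8/30) gives 7.1%, 13.9% and 20.4%. On that count a day-30 visit turns 20% into 1.20/(1 + 0.20/30) − 1 = 19.2%, and any later visit leaves 20% intact. Across other assumed shares, with g = 20%:

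| f | Observed change |
|---|---|
| 0% | 20.0% |
| 5% | 18.8% |
| 25% | 14.3% |
| 50% | 9.1% |
| 100% | 0% |

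**4. 6-minute walk.** It is measured at enrollment (V0), listed ahead of randomisation (V1), and again at 6 months. Steps 1 to 3 do not apply to it.

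**5. Precision.** At 20:10, the between-arm difference detectable with 80% power at two-sided 0.05 is (1.96 + 0.842) × √(1/20 + 1/10) = 1.09 SD (1.12 SD using the t distribution). At 18:9, after 10% dropout, it is 1.14 SD (1.19 SD using t). Only large differences would be detected, whatever reference is chosen.

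**The case against.** The strongest reply is that this is a randomised comparison of a multicomponent strategy. Objective 1 refers to Cardiac Compass-guided optimization, not to medication. The exercise steps are themselves set from CIED data, and Section 2 names missing exercise prescription as one of the problems being addressed. On that view the contrast estimates what it should, and separating the components was never the aim. This stands. A reader might infer that the comparison cannot answer objective 1, but the documents do not support that, because the randomised contrast validly estimates the effect of the package. What remains is a risk of misattribution, since much of the text describes the arm difference as medication alone.

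A reader might also take it as fact that the reference month falls after the intervention begins. That is not established. Under the implant reading, the month would ordinarily precede enrollment and there would be no dilution; the cost would be a less relevant baseline. Under the study-start reading, the month follows randomisation but may lie wholly before the first adjustment visit. The largest losses in the working are edge cases. They need every first visit at the earliest allowed day, or advice at an enrollment contact whose content is not described. They also need an instant full response, whereas Figure 1 describes movement toward a target.

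Finally, the schedule has no row for exercise targets. That does not show they go unrecorded, because the eCRFs are not in the documents. Control patients may also be advised on exercise by their own physicians, so the imbalance concerns study-delivered advice only.

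**Conclusion.** The firm defect is the missing anchor: the activity outcome refers to a discharge that the trial does not define, and the activity source is not named. Neither plausible reading gives a good baseline. Under the better-supported one, study start, the reference month is post-randomisation and 0% to 23% of it follows the first monthly visit. For an assumed 20% rise, the observed value then lies between 14.6% and the full 20%, and lower only if advice is given before that visit. This assumes a 30-day month and an immediate, sustained response; a gradual response loses less. Under the implant reading the loss is in relevance and precision, and the documents give no means of sizing it.

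It also holds that activity and 6-minute walk contrasts describe medication plus exercise advice together and cannot isolate medication optimization. The 6-minute walk baseline needs no change. These are secondary outcomes in a pilot of about 30 subjects and the primary endpoint is untouched, so the correction is worthwhile but does not put the trial in doubt.

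**What to change.** 1. Replace the reference month with mean daily CIED activity over a fixed window before randomisation, for example 30 days, or the available days where stored data are incomplete.
2. Compare month-6 CIED activity between arms, adjusting for that baseline, and write this into Section 17, which now has no analysis for the outcome. Keep Garmin activity descriptive, since it starts only at enrollment.
3. State beside objective 1 and the secondary outcomes that activity and 6-minute walk contrasts estimate the effect of the combined CIED-guided medication and exercise package. If the eCRF does not already do so, record study-delivered activity targets, and any exercise advice reported by controls, so that exposure can be described.
4. Replace the word discharge in the KCCQ outcome with enrollment, to match Section 2.

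The cost is protocol wording, possibly one eCRF field, and retrieval of stored device data. Every ICD will have been in place for at least 3 months and CIED acquisition is scheduled at enrollment, so earlier data should exist; the documents do not say how far back they can be retrieved, and this should be confirmed first. The other cost is a narrower claim under objective 1.

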- Blood samples may be taken as part of the study if a subject is randomized to the intervention group and the study team adjusts diuretic medications as clinically indicated. These blood samples are for patient safety and are routinely ordered to assess kidney function when a patient is taking diuretics. Labs will be ordered via a paper requisition and billed to the study. Research study staff will follow up within 3 days of result return.
- Future Use Blood Sample (optional)

Method of Assigning Subjects to Treatment

Study enrollment using the electronic data capture system that is available 24/7 to all study personnel. Patients will be randomized in a 2:1 fashion to either intervention or conventional management. Randomization will be conducted using a computer random number generator.

Follow-up Schedule (See also Table 1)

Following enrollment, all subjects will have scheduled follow-up visits (phone, electronic or telemedicine) by the study team at monthly intervals following enrollment and baseline testing.

CIED-derived physiologic and functional reports will be available to the study team only for patients assigned to the GDMT-medical optimization intervention group.

All subjects will be followed for a time-period of 6-months. Medical record data will be collected for a 12-month period.

The following time-points will be assessed:

- *Enrollment (V0):* Baseline clinical characteristics, existing echocardiographic measures and NYHA class will be recorded. Additional tests will include a 6-minute walk test and KCCQ questionnaire. Garmin wristband is provided.
- *Randomization (V1):* subjects will be randomized to an intervention arm of CIED-based medical optimization vs. conventional management.
- *Monthly virtual visits by research team (V1a):*
 - Conventional group: questions about symptoms, changes in activity levels, medications and adverse events. No additional CIED data provided to the subjects' usual clinical care providers since they will follow their own standard routine for CIED-monitoring.
 - Intervention group: virtual visits for medical optimization and prescription changes to medications based on CIED-reports and decision flowchart.
- *3-months (V2):*
 - Intervention group: office visit for clinical assessment, including physical exam and NYHA class. Clinical and adverse events.
 - Control group: office visit for device interrogation, medical record review, report any changes in standard care, NYHA class.
- *6-months (V3):*

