 - Intervention group: Physical exam, NYHA class, 6-minute walk test, KCCQ, clinical and adverse events.
 - Control group: office visit for device interrogation, medical record review, report any changes in standard care. NYHA class, perform 6-minute walk test and KCCQ.

The CIED and Garmin wearable wristband physiologic (activity, heart rate, oxygen saturation) and functional data will be continuously captured by the study's core lab for all patients throughout follow-up. The Garmin Wristband sensor data will not be used for intervention. The

lab/data capturing process is HIPAA compliant and Garmin wristband is identified through a study ID number and patient name is not registered into with wristband.

Timeline	Consent/ Enrollment (may be separate visits)	Performed Weekly	1m +- 7d	2m +- 7d	3m +- 7d	4m +- 7d	5m +- 7d	6m - 7d/+14d	Thru Month 12 Chart Review No Visits
Informed Consent	✓								
Randomization	✓								
Medical History	✓								✓
Vital Signs: BP, weight, RR	✓				✓			✓	
Review Inclusion/Exclusion Criteria	✓								
Medication List	✓		✓	✓	✓	✓	✓	✓	✓
Blood Sample Repository: Optional	✓								
Remote CIED data acquisition	✓	Data Acquired remotely throughout study							
Remote Wearable data (Garmin) acquisition	✓	Data Acquired remotely throughout study							
QOL: KCCQ	✓							✓	
Weekly E-Survey	✓	✓							
6MWT	✓							✓	
Virtual Visit	✓		✓	✓		✓	✓		
In-person Clinic Visit: Physical Exam NYHA Class CEID Interrogation	✓				✓			✓	

Medication Optimization – Management Regimen

The clinical research team managing the intervention group will follow standard clinical discretion in adjusting medications as appropriate and will use the medication flowchart (Figure 1) that includes considering the clinical physiologic data that is available in ICD devices and used clinically.

[figure not shown]
The medication adjustment flowchart reminds clinicians to consider any device data such as heart rates and activity etc. as well as patient reported outcomes to optimize medication dosing to meet guideline directed medical therapy which is associated with long term survival benefit.

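### The 6-minute walk outcome has no stated model: baseline-adjusted ANCOVA would be more precise, and the plan should say how month-6 walks missed at remote visits are handled

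*Combined protocol and SAP*

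**What the plan says.** Section 4 (Study Design) lists the walk among the secondary outcomes as "Mean changes in functional status (measured by 6-minute walk distance) in the intervention vs. control groups". It does not say how the means are to be compared.

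Section 7 (Study Procedures) places the walk at two times only. At enrolment: "Additional tests will include a 6-minute walk test and KCCQ questionnaire". At month 6 in the intervention arm: "Intervention group: Physical exam, NYHA class, 6-minute walk test, KCCQ, clinical and adverse events". At month 6 in the control arm, at an office visit: "NYHA class, perform 6-minute walk test and KCCQ". The 3-month entry has no walk ("Intervention group: office visit for clinical assessment, including physical exam and NYHA class"), and the schedule table agrees. There is therefore one post-baseline value per patient.

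In Section 4, the descriptions of both arms make the 3- and 6-month clinic visits conditional: "if in-person visit is not feasible, Zoom or telephone visit will be conducted". No remote walk, make-up test or substitute measure is described. The month-6 window in the schedule table is 7 days before to 14 days after, and Section 4 ends study visits at 6 months.

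Section 17 (Data Analysis Plan) covers the chi-square test of the primary outcome and the negative binomial analysis of recurrent medication changes. It says nothing about the walk: no model, covariates, analysis set, missing-data method or sensitivity analysis. Section 13 (Subject Withdrawals) only allows data to be used up to withdrawal.

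**The concern.** Two things are at stake, and the first is the firmer.

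**Precision.** With no model named, the natural reading of a mean-change outcome is a two-group comparison of raw changes. That comparison leaves unused the information in the baseline walk, which the trial already collects. With about 30 patients split 2:1, and about 27 evaluable after the 10% dropout allowed in Section 17, this matters.

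**Possible bias.** A patient seen by Zoom or telephone at month 6 has no planned way to contribute a follow-up walk. Patients who cannot attend may be the less mobile ones. Change from baseline is correlated with baseline, so if loss depends on baseline distance and does so differently in the two arms, raw mean change among those tested is shifted. The walk is more exposed to this than other measures, because KCCQ is completed in the app and device and wristband data are acquired remotely.

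**Working it through.** The plan gives no SD, correlation, effect or missing rate for the walk, so there is no stated figure to reproduce. The following are assumptions: SD 100 m at both times, no true effect, and baseline-to-follow-up correlation ρ from 0.5 to 0.8. The allocation of 10 control and 20 intervention patients follows from about 30 at 2:1.

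**1. Precision.** The change-score variance is proportional to 2(1−ρ) and the ANCOVA variance to 1−ρ². Their ratio is (1−ρ²)/[2(1−ρ)] = (1+ρ)/2, which gives 0.75, 0.80, 0.85 and 0.90 at ρ = 0.5, 0.6, 0.7 and 0.8. Estimating the slope in a small sample multiplies this by about (N−3)/(N−4). At N = 27 that is 24/23 = 1.043, so the ratios become about 0.78, 0.83, 0.89 and 0.94. The gain remains, but is modest at high ρ.

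**2. Bias if loss depends on baseline.** Let a share m of the lowest third of baseline distance be missing.

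- In SD units, the mean baseline of the lowest third is −1.091 and of the rest 0.545.
- The mean baseline of those tested is [(1−m)/3 × (−1.091) + 2/3 × 0.545]/(1−m/3).
- At m = 60% this is 0.273, at 30% it is 0.121, and at 15% it is 0.057.
- Expected change given baseline z is (ρ−1)z, so the bias (intervention minus control) is (1−ρ) × (control mean − intervention mean) × 100 m.

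Extreme scenario, 60% in control v 15% in intervention: (1−ρ) × (0.2727 − 0.0574) × 100 = (1−ρ) × 21.5 m. Overall missingness is then 20% v 5%, leaving 8 and 19 tested. The SD of change is 100√[2(1−ρ)], and the standard error is that times √(1/8 + 1/19) = 0.421.

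| ρ | Bias (m) | SE (m) | Bias/SE |
|---|---|---|---|
| 0.5 | 10.8 | 42 | 0.26 |
| 0.6 | 8.6 | 38 | 0.23 |
| 0.7 | 6.5 | 33 | 0.20 |
| 0.8 | 4.3 | 27 | 0.16 |

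The direction favours intervention, because low-baseline controls, who would tend to improve by regression to the mean, drop out of the comparison. By normal approximation the two-sided false-positive rate rises from 5.0% to between 5.3% and 5.8%.

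Milder scenario, 30% v 15%: (1−ρ) × (0.1212 − 0.0574) × 100 = 3.2 m at ρ = 0.5, falling to 1.3 m at ρ = 0.8. With equal missingness by baseline third, the bias is 0.

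Under these mechanisms ANCOVA bias is about 0, because loss depends only on the covariate. Simulating the extreme scenario at 10/20 randomised confirms this. It also shows the standard error falling from about 42 to 38 m at ρ = 0.5 and from about 33 to 31 m at ρ = 0.7.

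**3. Bias if loss depends on what happens after baseline.** Let D be the mean change in tested patients minus that in missing patients, in SDs of change. The bias of the mean-change comparison is m_I·D_I − m_C·D_C, where m is now the share of the whole arm that is missing. With 10% missing in one arm and 20% in the other, and D = 0.5 to 1.0 in both, it is 0.05 to 0.10 SD. With 10% and 30% it is 0.10 to 0.20 SD. The sign depends on which arm loses more. For comparison, the standard error at 9 and 18 tested is √(1/9 + 1/18) = 0.41 SD. Baseline adjustment removes only the part of this bias that baseline explains.

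**The case against.** The strongest reply is that the plan names an outcome, not an estimator. ANCOVA also estimates a difference in mean change, so nothing in the wording commits the sponsor to an unadjusted comparison or to patients with complete data. That stands: the gap is an unspecified analysis, and a reader who infers that a biased analysis has been chosen goes further than the text.

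It also stands that the remote-visit rule is the same in both arms, with the same schedule of contacts. A reader might infer that controls will lose more walks, since only the intervention team adjusts treatment. The documents give no rate of remote month-6 visits in either arm, so the 60% v 15% split is purely illustrative. At this sample size it means about two missing controls and one missing intervention patient.

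Several features limit the loss. There is already a three-week window at month 6. Section 12 pays $50 per completed clinic visit and covers parking. Section 4.1 excludes non-ambulatory NYHA class IV patients, unstable patients and those with a recent heart failure hospitalisation. Device-recorded activity, another functional secondary outcome, is acquired remotely. The walk is one unpowered secondary outcome in a pilot, and the primary outcome does not need attendance.

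None of this answers the precision point, or explains what happens when the month-6 visit is remote.

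**Conclusion.** The point holds as a gap in specification with a near-free improvement available. An unadjusted comparison of mean change would be less precise than ANCOVA: the variance ratio is 0.75 to 0.90 for assumed correlations of 0.5 to 0.8, or about 0.78 to 0.94 once the small sample is allowed for.

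The month-6 walk may be lost at a remote visit. The documents do not show that it will be, or how often. Bias is therefore conditional and of unknown size: zero if loss follows the same pattern in both arms, and about 4 to 11 m in an extreme scenario with SD 100 m, which is 0.16 to 0.26 of the standard error. Two stronger readings are not supported. One is that the trial is likely to show a spurious walk difference. The other is that ANCOVA would cure the missing-data problem; it does so only for loss explained by baseline distance, not for patients who miss the walk because they have deteriorated since.

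KCCQ does not share the attendance problem, because it is completed in the app. The case for adjusting it is precision alone.

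**What to change.** In Section 17, state that month-6 6-minute walk distance will be analysed by ANCOVA on arm with baseline distance as covariate. Do the same for the month-6 KCCQ score, for precision only.

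State how a remote month-6 visit is handled for the walk, and report missing walks by arm with reasons. Add a sensitivity analysis for walks missing because of death or deterioration, for example a worst-rank analysis for patients who died or could not walk.

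Optionally, allow a late walk at the next in-person contact within a stated limit, flagged as late. This would need an exception to the rule that study visits end at 6 months.

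The cost is a few lines of analysis text and one degree of freedom and, if the late test is adopted, some spread in test timing. No additional baseline measurement is needed.
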